8.3 As Exposed Exercise Compliant Set

The As Exposed Exercise Compliant Set (AEECS) consists of all randomized subjects who have at least one valid non-safety assessment after randomization, specifically we have

- post-randomization product (cigarette or IQOS) use experience if randomized to IQOS, • IQOS-2 or cigarette arm or
- no product use if randomized to the SA arm,

and who attended at least 34 of 38 (~90%) of the exercise training sessions except the subjects in IQOS-2 arm. Subjects in the IQOS-2 will be analyzed as exposed as they did not participate in the training. The AEECS will be analyzed by actual exposure (product use exposure, actual study arm).

Due to technical issues with the bike training equipment during the study, these rules are used to determine if a subject completed a training session for the purposes of defining the AEECS analysis set in addition to information regarding whether a training visit was done or not. We define a training session to be completed if a minimum of 20 or more minutes of exercise was done. If the training time is unknown then the session is considered to be not done. These checks from the protocol deviation dataset will be done regardless of whether data from the exercise training is available or not.

For a training session to be considered as not done from the protocol deviations (PD) dataset, the PD description will be checked for the following,

- "Bike training was not done" •
- "Bike training was partially completed for less than 20 min ..."
- "Bike training was partially completed for unknown number of minutes ..."

A bike training session is considered as complete if the following description for bike training is provided in the PD dataset,

- "Bike training was completed..."
- "Bike training was partially completed for at least 20 min..." •

In the case where there are inconsistencies between the PD dataset and bike training data, ie, for example bike training was marked as complete but the PD descriptions says otherwise, the PD rules will be used to determine completion of a bike training session.

Confidentiality Statement

Philip Morris Products SA.	Statistical Analysis Plan	Confidential
P1-EXC-01-EU	Final 2.0	Page 32 of 71
Related to PMI-RRP-WKI-112487		

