# IQOS and cigarette arms:

The switch to different variants of HeatSticks as well as the use of other tobacco- or nicotinecontaining products will not lead to discontinuation.

SA arm:

The use of any tobacco- or nicotine-containing products will not lead to discontinuation.

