Missing data for self-reported daily use will not be imputed and we will assume that the derived average monthly use from non-missing data is representative of the actual usage. For each analysis period (Week 1 or Overall), if more than 50% of product use data is not available then the subject will be grouped into the 'Others' product use arm. Therefore, it is possible that a subject is not considered for statistical modelling as it is grouped into 'Others' for Week 1 (3 out of 7 days of product use data only) but available for analysis for the entire study period if more than 50% of product use data was eventually collected throughout the study. A subject may have switched product use groups throughout the study and the total number of subjects in an arm may fluctuate over time depending on the actual product use.

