6 SAMPLE SIZE JUSTIFICATION

The sample size of 20 per arm (smoking abstinence with training, IQOS with training, continued cigarette smoking with training) was determined based on previously published results, which reported a standard deviation of 14 mL/kg/min in VO₂max in the change

Confidentiality Statement

Philip Morris Products SA.	Statistical Analysis Plan	Confidential
P1-EXC-01-EU	Final 2.0	Page 30 of 71
Related to PMI-RRP-WKI-112487		SAD DI EYC OI EU

between groups which continued smoking and those who were smoking abstinent after participating in a 12-week training program (Albrecht, et al. 1998). This sample size allows a probability of 90% that the half-width of the 95% confidence intervals between two arms have a precision of approximately 10.3 mL/kg/min.

For example, if the mean difference in change between the cigarette arm and smoking abstinence arm was 12 mL/kg/min after training, we expect that if the experiment were repeated many times then on average 90% of the time the 95% confidence intervals of the mean differences between two arms will be within 1.7 and 22.3. To allow for a dropout rate of approximately 20%, the sample size will be 25 per arm. The IQOS-2 arm without training will mainly serve as a secondary analysis to the IQOS-1 arm with training, and the drop-out rate in this arm is expected to be lower. Therefore, only 15 subjects will be randomized to this arm.

CHANGES FROM THE PROTOCOL SPECIFIED STATISTICAL 7 ANALYSES

An exploratory analysis of VO2max and exercise capacity will be carried out on subjects with additional biochemical verification of smoking status.

8 **ANALYSIS SETS**

The main population for non-safety analysis will be the As Exposed Exercise Compliant Set. Safety will be analyzed using the Safety Set.

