8.1 Full Analysis Set

The Full Analysis Set (FAS) consists of all randomized subjects who have at least one postrandomization product (cigarette or IQOS) use experience if randomized to IQOS, IQOS-2 or cigarette arm, and who have at least one valid non-safety assessment after randomization. All subjects in the SA arm who fulfil these requirements, except the product use experience, are part of this set as well. The FAS will be analyzed by randomized study arm.

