8.4 As Exposed Biochemically and Exercise Compliant Set

A subset of the AEECS based on biochemical verification of smoking status (AEBECS) will be analysed based on actual arm as determined with these additional criteria.

For a subject to be classified as smoking abstinent, in addition to the product use diary with an average cigarette use at max 5 Cigarettes/month the following will be used,

- No CO breath test > 6 ppm at three consecutive visits from V3 onwards.
- Total NNAL concentration < 75.9 pg/mL in spot urine (Berg, et al. 2012) at two or more visits collected from V3 onwards.
- CEMA concentration adjusted for creatinine < 40 ng/mg creat (Claussen, et al. 2019) in spot urine at two or more visits collected from V3 onwards.

The following biochemical verification will be used in addition to the product use diary to further fine tune subjects in the IQOS user group.

- No CO breath test > 6 ppm at three consecutive visits from V3 onwards.
- Total NNAL concentration < 75.9 pg/mL in spot urine at two or more visits collected from V3 onwards.
- CEMA concentration adjust for creatinine < 40 ng/mg creat in spot urine at two or more visits collected from V3 onwards.

8.5 **Protocol Deviations**

All protocol deviations will be listed and also summarized based on the classification of deviation type for subjects in the Safety Set.

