9.4 Measurement of Product Compliance

There is no restriction on allocated product use.

Although subjects are being requested to use solely the product allocated to their respective study arm, it is considered that not all subjects randomized to the IQOS arms or to the cigarette arm will exclusively use the randomized product at all times during the study. Subjects may concomitantly use IQOS and cigarettes (dual use). To account for dual use of IQOS and cigarettes, adjustments for cigarette or IQOS use outside of the intended arms will be done statistically. Similarly, it is expected that subjects in the SA arm who should stay abstinent during the study may relapse to the use of tobacco or nicotine-containing tobacco products (e.g., cigarette or IQOS). In addition to the randomized arms of IQOS, Cigarette or SA , additional arms comprising of the categories Dual-1 and Dual-2 according to the definition in Section 9.1.1 "Stratified Presentation" will be used in part of the analysis. Subjects in the 'Others' product use group (Figure 2) will only be listed and not analyzed.

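### As written, the main analysis set drops any subject randomised to smoking abstinence (SA) who reports a single cigarette or HeatStick, while non-adherent subjects in the other arms are kept and regrouped by exposure

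*SAP*

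**What the plan says.** SAP section 8 states: "The main population for non-safety analysis will be the As Exposed Exercise Compliant Set". Section 8.3 admits subjects from the IQOS and cigarette arms once they have any post-randomisation use of either product. For the abstinence arm the condition is "no product use if randomized to the SA arm". Protocol 12.4.1 has the same bullet. Section 8.3 then says: "The AEECS will be analyzed by actual exposure (product use exposure, actual study arm").

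Other parts of the plan bear on this:

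- **SAP 9.4** foresees relapse: "it is expected that subjects in the SA arm who should stay abstinent during the study may relapse".
- **SAP 5.5.1** foresees regrouping: "A subject may have switched product use groups throughout the study".
- **Protocol 5.2**, for the SA arm: "The use of any tobacco- or nicotine-containing products will not lead to discontinuation". Lapsers therefore stay in the study and can provide V4 and V43 data.
- **SAP 8.4** classes a subject as abstinent on biochemical criteria applied "in addition to the product use diary with an average cigarette use at max 5 Cigarettes/month".
- **SAP 8.1**, for the Full Analysis Set (FAS), only waives the use condition: "All subjects in the SA arm who fulfil these requirements, except the product use experience, are part of this set as well".

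**The concern.** For SA, the set bullet makes the absence of use an entry condition. The FAS makes use unnecessary but does not forbid it. Under the AEECS wording a lapser leaves the set before any exposure grouping is applied, so the diary tolerance and the regrouping never reach subjects randomised to SA. The AEBECS is defined as a subset of the AEECS and inherits the exclusion.

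Selection on adherence to the assigned regimen therefore acts through set membership for one randomised arm only. Two kinds of subject are lost:

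- **Light lapsers**, who would still be classed as abstinent, disappear from the SA group.
- **Heavier relapsers** disappear from the dual, cigarette or IQOS groups to which their exposure belongs.

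The SA comparisons at V4 and V43 in SAP Tables 4 and 5 are affected by the first loss, and the other groups by the second. The bullet has no time window either, so on its wording a first lapse in the third month also removes the subject's V4 result.

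**Working it through.** **1. How each rule treats a post-randomisation deviation**

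| Subject | Entry to AEECS as written | Treatment after entry |
|---|---|---|
| Randomised to IQOS, smokes some cigarettes | Admitted (use of either product suffices) | Grouped by actual exposure |
| Randomised to cigarettes, uses HeatSticks | Admitted | Grouped by actual exposure |
| Randomised to SA, reports one cigarette or HeatStick | Not admitted | None |

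The training arms must also attend 34 of 38 sessions. That condition is common to all three and does not explain the difference.

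**2. What the diary tolerance allows**

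SAP 5.5.1 averages daily use and multiplies by 30. The tolerance in SAP 8.4 is 5 cigarettes a month.

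- V3 to V43 is 106 days: 5 × 106 / 30 = 17.7, or about 18 cigarettes.
- V3 to V4 is 7 days: one cigarette gives 1/7 × 30 = 4.3 a month (within the tolerance), and two give 8.6 (outside it).

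The bullet in SAP 8.3 allows none in either period. Applying the 5-a-month figure to the AEECS is an inference: it is written only in SAP 8.4, and the full categorisation is in Figure 2, which is not shown in the text available. How a few HeatSticks would be classed cannot be told for the same reason.

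**3. The plan's precision figure**

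Inputs from SAP section 6 and protocol 12.2: SD 14 mL/kg/min, 20 per arm, 95% interval, 90% assurance, stated half-width about 10.3.

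Half-width = t(0.975, df) × SD × √[χ²(0.90, df)/df] × √(1/n₁ + 1/n₂), with df = n₁ + n₂ − 2.

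For 20 against 20: 2.0244 × 14 × √(49.513/38) × √(2/20) = 2.0244 × 14 × 1.1415 × 0.3162 = 10.2. This reproduces the stated value. Inflating for 20% drop-out, 20/0.8 = 25 per arm, also as stated.

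**4. Illustration of the loss**

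The documents give no lapse rate, so the SA number below is an assumption. The comparator is 20 cigarette subjects.

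| SA subjects left | Light lapsers removed from 20 | 90%-assured half-width (mL/kg/min) |
|---|---|---|
| 20 | 0 | 10.2 |
| 18 | 2 | 10.6 |
| 15 | 5 | 11.2 |
| 10 | 10 | 12.9 |

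The last row is 2.0484 × 14 × √(37.916/28) × √(1/10 + 1/20) = 12.9. It is an upper bound for a 50% lapse rate, because it treats every lapse as light.

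**The case against.** **The bullet may be meant as a waiver.** It follows a list of what the set contains, it parallels the FAS wording, and the SAP plainly expects relapse. That reading is plausible and may be what was intended, but the words do not say it. Two programmers could build different main populations from the same text, and SAP version 2.0, which revised the training-completion rule for this set, left the bullet unchanged.

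**A reader might charge the whole fall from 20 to 10 SA subjects to this bullet.** The documents do not support that. With the bullet corrected, SAP 5.5.1 would still move relapsers above the tolerance out of SA. If ten of 20 completers lapse and five do so lightly, the corrected rule leaves SA at 15, not 20: half-width 11.2 against 20 cigarette subjects, or 10.6 if the other five join the cigarette group (15 against 25). If all ten are heavy relapsers, SA has 10 under either rule. Nor do the documents show that the SA arm will fall below 20 through lapses.

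**A reader might infer that a selected SA arm is compared with essentially unselected arms.** It is not. The cigarette and IQOS-1 arms face the same attendance rule, subjects with more than half of their diary data missing go to a group that is not modelled, and dual users are split off. Any as-exposed analysis selects on behaviour after randomisation. What stands is narrower: deviation leads to removal in one arm and to regrouping in the others.

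**A reader might infer that the analysed SA group holds only perfect abstainers.** That is true at most of those randomised to SA. Subjects from other arms with very little use might be classified into SA. The parallel bullet defines product as cigarette or IQOS, and nicotine replacement therapy is allowed on request, so its use alone need not exclude anyone.

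**There is a fallback.** The FAS keeps all SA subjects with a valid post-randomisation assessment, by randomised arm. SAP 9.6.1.3 makes FAS analyses optional, but SAP 13.2 lists FAS tables for VO₂max (15.2.2.1.6 to 15.2.2.1.10) and exercise capacity (15.2.2.2.6 to 15.2.2.2.10). The study is also descriptive, with no hypothesis test. Both points limit the damage, but the main population remains wrongly defined.

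**Conclusion.** The point holds in a limited form. As written, the main non-safety set and its biochemically verified subset remove every subject randomised to SA who reports any cigarette or HeatStick use. This conflicts with analysis by actual exposure in the same section, with the expectation of relapse in SAP 9.4, and with regrouping in SAP 5.5.1. It also conflicts with the 5-a-month criterion in SAP 8.4, if Figure 2 applies that criterion to the AEECS. The consequence is adherence selection specific to those randomised to SA.

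The precision cost to the SA group comes only from light lapsers and cannot be fixed from the documents. The range shown, 10.2 to at most 12.9 mL/kg/min, rests on SD 14, 20 completers per arm who also meet the attendance rule, and assumed lapse shares from none to half. The direction and size of any bias in the VO₂max contrasts are likewise not determinable from the plan.

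**What to change.** In SAP 8.3, replace the second bullet with: *product use (cigarette or IQOS) experience is not required if randomized to the SA arm*. This matches the FAS. Let SAP 5.5.1 assign SA lapsers to their actual exposure group in each analysis period, and state in the text of 5.5.1 the cigarette and HeatStick thresholds that define abstinence, so that sections 5.5.1, 8.3 and 8.4 agree.

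If zero use is truly intended, say so, give the period it covers, and justify treating SA differently from the other arms.

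Make the change before database lock and record it in SAP section 7 as a departure from protocol 12.4.1. A protocol amendment would have to go to the ethics committee (protocol 1.1), so the SAP route is the lighter one. The cost is one bullet, one entry in section 7 and a check of the set-derivation program. No new data are needed. The report should also point to the listed FAS tables for VO₂max and exercise capacity as the check by randomised arm.

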1.1 Revision History

Table should only include approved version and needs to be completed starting with version 1, the initial version of the document.

Version	Date of Revision	Revision
1.0	06 Dec 2019	Initial Version
2.0	09 Mar 2020	 Updated wording in formula for calculation of Nicotine Equivalents in 5.1.1. Added IPAQ scoring algorithm in 5.3.5 The calculation of product use categories is simplified to only be done for Week 1 and from V3 – V43 (Overall) or visit before early termination where applicable. For subjects with insufficient product use data they will be classified under the "Other" group per section 5.5.1. The definition of completion of a bike training is expanded to include cases where at least 20 minutes of training was done and also those which were done but without data due to technical issues. Added 9.1.7 to describe how to handle data which is implausible.

Confidentiality Statement

Philip Morris Products SA.

Statistical Analysis Plan Final 2.0 Confidential Page 6 of 71

Related to PMI-RRP-WKI-112487

P1-EXC-01-EU

SAP_P1-EXC-01-EU

Version	Date of Revision	Revision
		 Descriptive statistics for VO2_{max}, exercise capacity and other related endpoints will now include an acute and training baseline that is based on product use categories calculated at Week 1 and Overall, respectively, this is related to third bullet point above. Clarified the analysis in 9.6.1.1.2 for exercise capacity to include or exclude subjects which did not have the correct work load performed. Added a sensitivity analysis to assess the impact when all subjects including those with the wrong workloads are analysed. Removed some boxplots for VO₂max and exercise capacity based on subgroups. Added demographics for AEBECS Added tables for analysis sets and reason for exclusion from analysis sets and number of subjects in each analysis set. Added tables for exercise capacity, biological health markers and biomarkers of exposure for AEBECS. Removed some redundant listings and updated listing numbers. Fixed typos throughout document.

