9.6.1 Endpoint Analyses

The following non-safety endpoints will be analyzed using the AEECS considering the actual study arm (i.e. product use exposure). The following sections describe the statistical models used in analyzing the endpoints as well as descriptive statistics used for summarizing the data.

In general, for model based analysis all visit data will be used and analyzed within the same model.

- 9.6.1.1 Statistical Analysis of Endpoints
- 9.6.1.1.1 To evaluate changes in VO₂max in subjects switching to IQOS (with and without training), continuing to smoke cigarettes (with training) and being smoking abstinent

A linear mixed effects model will be used to estimate the difference in VO₂max between each arm (SA arm, IQOS-1+IQOS-2 combined arm, Dual-1+Dual-2 arm) versus cigarette arm one week after randomization (V4) and after completion (SA arm, IQOS-1 arm, IQOS-2 arm, Dual-1 arm) of the 12-week training program (V43). The degrees of freedom will be adjusted by using Kenward Roger (KR) method and the Saitterthwaite method will be used in case of convergence issues. Both V4 and V43 data will be used together in the same model. At V4, both IQOS-1 and IQOS-2 will be combined into a single IQOS group as these subjects did not attend any exercise training.

The dependent variable will be the VO₂max change from baseline with baseline VO₂max, arm, visit, sex, age and visit*arm as *fixed* covariates and subject fitted as a random effect. In addition, the following *exploratory* covariates BMI, RPC, COHb levels at each visit, cigarette consumption at V1, IPAQ score at V1, average step count 2 weeks prior to visit, self-reported daily cigarette consumption (from randomization until each visit), cigarette smoking 30-60 minutes before test for subjects in cigarette arm and IQOS use 30-60 minutes before test for subjects in IQOS arm will be assessed for adequacy in the model using a step-wise (backward) approach through the following algorithm.

Data and information contained in this document are considered to constitute trade secrets and confidential commercial information, and the legal protections provided to such trade secrets and confidential information are hereby claimed under the provisions of applicable law. No part of this document may be publicly disclosed without the written consent of Philip Morris Products S.A

Philip Morris Products SA.	Statistical Analysis Plan	Confidential
P1-EXC-01-EU	Final 2.0	Page 40 of 71
Related to PMI-RRP-WKI-112487		

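### The main V4 (acute) results for VO2max and exercise capacity keep trained-arm subjects only if they later complete 34 of 38 training sessions, while IQOS-2 is exempt and pooled in unfiltered

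*SAP*

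**What the plan says.** Protocol 12.4 and SAP section 8 name the AEECS as the main population for non-safety analyses. Besides its product-use and valid-assessment conditions, SAP 8.3 requires attendance: "and who attended at least 34 of 38 (~90%) of the exercise training sessions except the subjects in IQOS-2 arm". SAP 9.6.1 applies this set to the endpoint models: "The following non-safety endpoints will be analyzed using the AEECS considering the actual study arm (i.e. product use exposure").

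VO2max and exercise capacity are each fitted with V4 and V43 in one model. The acute contrasts are "between each arm (SA arm, IQOS-1+IQOS-2 combined arm, Dual-1+Dual-2 arm) versus cigarette arm one week after randomization (V4"). The reason given for pooling is this: "At V4, both IQOS-1 and IQOS-2 will be combined into a single IQOS group as these subjects did not attend any exercise training".

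In SAP 13.2 the AEECS V4 tables for both endpoints carry the topline flag. FAS V4 tables (15.2.2.1.6 for VO2max, 15.2.2.2.6 for exercise capacity) are listed without it. SAP 8.1 analyses the FAS by randomised arm, and SAP 9.6.1.3 makes FAS analyses conditional on being judged appropriate. The AEBECS is a subset of the AEECS (SAP 8.4), so it carries the same attendance rule.

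**The concern.** The V4 test is meant to show what one week of switching or abstinence does before any training. Whether someone later completes 34 sessions cannot have affected that test, yet it decides whether the test counts in the main result. A trained-arm subject with a valid V4 test who stops training in, say, week 6 leaves the acute estimate. SAP 9.1.4 says dropouts are analysed wherever data are available, but this rule removes their V4 data from the main set.

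The filter is also uneven. Cigarette and SA are filtered in full. The pooled IQOS group mixes filtered IQOS-1 with unfiltered IQOS-2, and pooled Dual mixes Dual-1 with Dual-2 in the same way. The SAP's own reason for pooling is that training has not started by V4. That is equally a reason for training attendance not to define the V4 population.

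At stake is what the acute estimate describes. As defined, it concerns later exercise completers in the trained arms plus all eligible IQOS-2 subjects, not everyone tested at V4.

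**Working it through.** **Timing** (Protocol synopsis and 4.1; SAP 4.1). V4 is 7±2 days after V3, so day 9 at the latest. V5, the first session, is 15±2 days after V3, so day 13 at the earliest. Protocol 9.4.2 also starts training 7±1 days after V4. All 38 sessions follow V4.

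**The plan's own figure** (SAP section 6). With SD 14, n = 20 per arm and 90% probability, the half-width is t(0.975, 38) × 14 × √(χ²(0.90, 38)/38) × √(2/20) = 10.23, against about 10.3 stated. The dropout allowance is 20/0.8 = 25 per arm. Both reproduce, and neither is in dispute.

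**Precision at V4.** Assume 20% of each trained arm fails the rule (25 to 20) and all who fail have V4 data. The 20% is borrowed from the dropout allowance; the documents give no failure rate for the rule. The n are randomised n, and actual product-use groups will differ. Standard errors are in SD units.

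| Contrast | Formula | Without rule (n = 25) | With rule (n = 20) | Ratio |
|---|---|---|---|---|
| SA v cigarette | √(2/n) | 0.2828 | 0.3162 | 1.118 |
| Pooled IQOS v cigarette, weights 0.5/0.5 as in the example SAS code | √(0.25(1/n + 1/15) + 1/n) | 0.2582 | 0.2814 | 1.090 |
| Pooled IQOS v cigarette, weighted by n | √(1/(n + 15) + 1/n) | 0.2550 | 0.2803 | 1.099 |

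How far this depends on the failure rate: if sessions were attended independently (an assumption) with probability 0.90, 0.92 or 0.95, the share reaching 34 of 38 would be 67%, 82% or 96%. The SA v cigarette ratio, 1/√(share kept), would then be 1.22, 1.11 or 1.02.

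**Bias, conditional only.** Let f be the failing fraction and D the mean V4 change in subjects who meet the rule minus that in subjects who fail it. The retained mean minus the full mean is f·D. With f and D equal across the trained arms:

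- SA v cigarette: f·D − f·D = 0.
- Pooled IQOS v cigarette, 0.5/0.5 weights: 0.5·f·D − f·D = −0.5·f·D.
- Pooled IQOS v cigarette, weighted by n at 20% loss: (20/35)·f·D − f·D = −0.43·f·D.

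The documents say nothing about D. For assumed D of 0.25 to 1.0 SD and f = 0.2, the pooled shift (0.5/0.5 weights) is 0.025 to 0.10 SD, or 0.09 to 0.36 of its standard error of 0.281. SA v cigarette shifts only if attendance, or its relation to V4 change, differs by arm. For example, 8 v 3 of 25 failing with D = 0.5 SD gives (0.32 − 0.12) × 0.5 = 0.10 SD. Against a standard error of √(1/17 + 1/22) = 0.323, that is 0.31 SE. If D = 0 there is no bias anywhere.

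**Coverage by listed analyses** (SAP 13.2). No listed V4 analysis groups by actual use without the attendance rule. The V4 respiratory, body fat and waist, and exposure-marker outputs have no FAS version.

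**The case against.** The plan already contains V4 analyses without the rule. SAP 13.2 lists a full FAS block for both endpoints. Read with SAP section 1, which says the document lists the study's tables, the conditional wording in 9.6.1.3 may mean only that these are the analyses selected. Grouping by randomised arm at one week keeps the randomised comparison, which is a strength. The AEECS was prespecified in the protocol. A single cohort across V4 and V43 fits a joint model. The study is descriptive, with no hypothesis tested and no multiplicity control.

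Much of this stands. The FAS tables are a real safeguard for VO2max and exercise capacity, and a common cohort is a defensible secondary view. But the FAS changes population and grouping together, so it cannot isolate the effect of the attendance rule. It is not topline and does not reach the other V4 outputs. A descriptive study still reports the figure as the acute effect, so the population should match that label.

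Two stronger readings are tempting. A reader might infer that the acute result is biased, perhaps for or against IQOS. The documents do not show that attendance differs by product or relates to V4 change, so neither the presence nor the direction of bias can be claimed. A reader might also infer that the trial falls short of its planned precision. It does not: the plan was sized at 20 per arm, so the gain at V4 is recoverable precision, not the repair of a shortfall.

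**Conclusion.** The point holds as a matter of definition. The main and topline V4 estimates for VO2max and exercise capacity are conditioned on behaviour after the measurement, unequally across groups, and they leave out valid V4 data. Under the 20% assumption, with all failing subjects tested at V4, the standard error is about 12% higher than it need be for SA v cigarette and 9-10% higher for pooled IQOS v cigarette. If some subjects leave before V4, the recoverable part is smaller. Any bias depends on an unknown relation between attendance and V4 change. This is a cheap improvement: it does not invalidate the plan and does not touch the V43 result.

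**What to change.** Make the main V4 result a separate V4-only model for each of the two endpoints. Include all subjects with a valid V4 test who meet the other AEECS conditions, drop the 34-of-38 rule, and group by Week 1 product use. Use the same covariates as the joint model; the visit terms and the subject random effect fall away with one record per subject.

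Take the V43 estimates from the existing AEECS joint model. Do not instead keep non-completers' V4 records in the joint model while deleting their V43 records. With within-subject correlation ρ, that would move the trained-arm V43 mean by about −ρ·f·D. At assumed values ρ = 0.5, f = 0.2 and D = 0.5 SD this is −0.05 SD, as large as the V4 shift being removed (0.5 × 0.2 × 0.5 = 0.05), and it would not cancel against unfiltered IQOS-2.

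Report the current AEECS V4 estimate as a sensitivity analysis, labelled as an estimate among later exercise completers. Present FAS Tables 15.2.2.1.6 and 15.2.2.2.6 beside the V4 result. Drop the rule likewise for the other V4 AEECS outputs: respiratory parameters, VO2 and heart rate, RPC, body fat and waist, and exposure markers. Record the change in SAP section 7, because the protocol defines the AEECS and names it the main set.

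The cost is SAP wording and re-run V4 tables, with no new data. The downside is that V4 and V43 rest on different subjects. SAP 5.5.1 already accepts this in part, since a subject may be absent from Week 1 modelling yet analysed for the whole study.
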